Blood sampling and measurement will be performed for reticulocytes (counts and fractions) on the first day of the screening period, the first day of the treatment period, Weeks 2, 4, 6, 8, 10, 12, 16, 20, 24, 28, 32, 36, 40, 44, 48, and 52 of the treatment period, and the day of discontinuation of treatment.

(12) EPO (MT-6548 group only)

Blood sampling and measurement of EPO will be performed on the first day of the treatment period, treatment period Weeks 2, 4, 6, 12, 24, 36, and 52, and the day of discontinuation of treatment. Blood sampling time will be recorded in CRFs.

(13) QOL measures (EQ-5D-5L, KDQOL)

Subjects will fill out EQ-5D-5L and KDQOL questionnaires (Appendices 4 and 5) on the first day of the treatment period, treatment period Weeks 12, 24, and 52, and the day of discontinuation of treatment, and results recorded in CRFs.

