the treatment period.)" should be conducted for subjects continuously using iron supplements or iron-containing phosphate binders and subjects never using iron supplements and iron-containing phosphate binders during the treatment period. Analysis should be performed only in the MT-6548 group, and no analysis using the MMRM model will be conducted for patient cohorts. However, subjects who uses intravenous iron at least once should be excluded from the tabulation.

Since intravenous iron should be included in the tabulation for treatment period phase 1, the tabulation for treatment period phase 1 should be output again.

7) Analysis by iron supplements and iron-containing phosphate binders formulations

An analysis similar to "1) Treatment period Hb at each evaluation time point in the treatment period" except for the analysis using the MMRM should be conducted for subjects continuously using iron supplements or iron-containing phosphate binders during the treatment period. Analysis should be performed only in the MT-6548 group, and no analysis will be performed for patient cohorts. However, subjects who uses intravenous iron at least once should be excluded from the tabulation.

8) Analysis of Hb value at Week 52 and CRP values on the first day of the treatment period

For MT-6548 group only, a scatter plot chart should be provided after linear regression with the following variables. No analysis will be performed for patient cohorts.

x: Logarithmic CRP value on the first day of the treatment period

y: Hb values at Week 52 of the treatment period

(3) Proportion of subjects whose Hb level during the treatment period is within the target range (11.0 g/dL to <13.0 g/dL) or outside the target range (<10.0 g/dL or ≥ 13.0 g/dL)

The number, proportion, and 95% CI (Clopper-Pearson [Exact] method) of subjects with Hb value within the target range (11.0 g/dL to <13.0 g/dL, within), <11.0 g/dL (below), and ≥ 13.0 g/dL (above) at each time point of the treatment period should be provided by treatment group. McNemar tests should be used for before and after comparison (ratio of subjects within the target range and out of target range) on the first day and each evaluation time point of the treatment period.

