For Index value and VAS score, descriptive statistics of measured values and descriptive statistics of changes from the first day of the treatment period should be provided for each treatment group at each evaluation time point. A paired t-test should be performed for before and after comparison of changes from the first day of the treatment period.

A group comparison should be conducted for the changes in Index value and VAS score from the first day of the treatment period at each evaluation time point using the MMRM (with compound symmetry [CS] for a covariance matrix within subject variance). LSMean, its standard errors, and 2-sided 95% CI should be calculated, and the point estimate, its standard errors, 2-sided 95% CI, and p-value should be provided for the group difference (MT-6548 – darbepoetin) of the LSMean by treatment group.

The correlations of Hb value and Index Value, and Hb value and VAS score at all evaluation time points should be evaluated using linear regression and Emax model. For linear regression, the estimated items analyzed by the following model (refer to “linear regression model”) should be output, and the p-value of the test with 0 slope as the null hypothesis should be calculated. Scatter plots and regression lines should be prepared separately for each treatment group. On the Emax model, estimated items (refer to “Emax model”) analyzed by the following model should be output. Scatter plots and regression curves should be prepared separately for each treatment group. No analysis will be performed for patient cohorts.

The correlation between the change in Hb from the first day of the treatment period and the change in Index Value from the first day of the treatment period and the correlation between the change in Hb from the first day of the treatment period and the change in VAS score from the first day of the treatment period should be analyzed in linear regression in the same way as the correlation between Hb value and Index Value and between Hb value and VAS score, respectively. Only the Correction and Conversion (Hb <11.0 g/dL) cohorts should be analyzed

[Linear regression model]

regression equation $Y = aX + b$

X: Hb value, or change in Hb value from the first day of the treatment period

Y: Index Value, or VAS score, or change from the first day of the treatment period on the left

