Estimated items (output item): a: slope of the regression line and its standard error, b: intercept of the regression line and its standard error, r: correlation coefficient

[Emax model]

Model 4-parameter logistic model

X: Hb value

Y: Index Value or VAS score

Estimates (output item): EC₅₀ with its standard errors and 2-sided 95% CI, Emax with its standard errors and 2-sided 95% CI, min with its standard errors and 2-sided 95% CI, slope with its standard errors and 2-sided 95% CI, R-Square (contribution ratio).

KDQOL

Descriptive statistics of KDQOL should be calculated by subscale (Section 4.13 [Table 4.13.2] “subscale”) for measured values and changes from the first day of the treatment period at each evaluation time point by treatment group. Scores by subscale should be calculated using a scoring method (Section 4.13). Scores by subscale should be calculated using a scoring method (Section 4.13). A paired t-test should be performed for before and after comparison of changes in KDQOL from the first day of the treatment period.

A group comparison should be conducted for the change in KNDQOL from the first day of the treatment period at each evaluation time point using the MMRM (with compound symmetry [CS] for a covariance matrix within subject variance). The point estimate of LSMean, its standard errors, and 2-sided 95% CI should be calculated by treatment group, and the point estimate, its standard errors, 2-sided 95% CI, and p-value should be provided for the group difference (MT-6548 – darbepoetin) of the LSMean.

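### The Hb-versus-EQ-5D-5L regressions appear to pool repeated visits without a subject term, so their standard errors and p-values are not valid and are likely too small

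*SAP*

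**What the plan says.** In the Final SAP, 8.5.2 (14), the relation of Hb to the EQ-5D-5L index value and VAS is handled as follows: "Hb value and VAS score at all evaluation time points should be evaluated using linear regression and Emax model". The linear model is Y = aX + b, with Hb as X and the index or VAS as Y. The outputs are "a: slope of the regression line and its standard error", the intercept with its standard error, and one correlation coefficient. In addition, "the p-value of the test with 0 slope as the null hypothesis should be calculated". The only split is by arm: "Scatter plots and regression lines should be prepared separately for each treatment group". The Emax model, described as a 4-parameter logistic, yields standard errors and 95% CIs for each parameter. A further set of regressions relates change in Hb to change in index and VAS in the same way, in the Correction and Conversion (Hb <11.0 g/dL) cohorts only. The Phase 1 SAP, 8.5.3 (14), has matching text.

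Protocol 9.2.3 (13) schedules the questionnaires on the first day of treatment and at "treatment period Weeks 12, 24, and 52, and the day of discontinuation of treatment, and results recorded in CRFs".

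**The concern.** One subject's Hb values at different visits tend to resemble each other, and so do that subject's QOL scores. If several visits per subject enter one ordinary regression, the software counts them as separate pieces of information. When both variables are positively correlated within subject, the slope looks more precise than it is and the zero-slope test rejects too often. The same applies to the Emax standard errors and intervals.

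In the text of the SAPs these are the only analyses that relate Hb to quality of life, and they carry p-values. A slope that is only chance could look better supported than it is.

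**Working it through.** **Is pooling the right reading?** Neither SAP says it in words. Three features of the text point to it.

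- For the group comparison of the same EQ-5D-5L scores, the Final SAP writes "at each evaluation time point using the MMRM (with compound symmetry [CS] for a covariance matrix within subject variance"). That is visit by visit, with within-subject correlation modelled. The regression text changes *each* to *all* and drops the covariance.
- Where one point per subject is meant, the visit is named. The CRP regression in 8.5.1 (2) 8) has "y: Hb values at Week 52 of the treatment period", and the ferritin regression in 8.5.2 (10) also uses Week 52.
- The regression outputs are one slope, one intercept and one correlation. None is indexed by visit.

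**Points per subject.** The scheduled QOL visits are the first day and Weeks 12, 24 and 52. That gives m = 3 in Phase 1 and m = 4 in the final analysis. Change from the first day uses up the baseline, so the change fits have at most 2 or 3 scheduled pairs.

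**Size for the Hb-level fits.** The SAPs give no figure for this regression, so there is nothing to reproduce. With ρx the within-subject correlation of Hb and ρe that of the QOL residual (both assumed, because the documents give neither):

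- design effect DE = 1 + (m − 1) × ρx × ρe
- true SE ÷ reported SE = √DE
- actual type I error = 2 × [1 − Φ(1.96 / √DE)]

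| ρx, ρe | m = 3: DE, SE ratio, type I error | m = 4: DE, SE ratio, type I error |
|---|---|---|
| 0.2, 0.6 | 1.24, 1.11, 7.8% | 1.36, 1.17, 9.3% |
| 0.3, 0.7 | 1.42, 1.19, 10.0% | 1.63, 1.28, 12.5% |
| 0.4, 0.7 | 1.56, 1.25, 11.7% | 1.84, 1.36, 14.8% |
| 0.5, 0.8 | 1.80, 1.34, 14.4% | 2.20, 1.48, 18.6% |

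Simulation of ordinary least squares with 150 subjects, no true association and the same four pairs gave 8.0, 9.9, 12.4 and 14.7% for m = 3. For m = 4 it gave 8.7, 12.5, 14.5 and 18.4%.

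**When Hb rises after baseline.** Suppose every subject's Hb rises by an assumed 1.5 within-visit SDs after baseline (150 subjects, m = 4, ρe = 0.6):

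| ρx | SE ratio | Type I error |
|---|---|---|
| 0.3 | 1.11 | 7.6% |
| 0.1 | 0.98 | 4.3% |
| 0 | 0.92 | 3.3% |

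So the pooled SE can also be about right or slightly too large.

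**Change-versus-change fits.** The Correction target is 100 subjects, so about 50 per arm. Two changes that share a baseline are correlated 0.5 if all visits are equally correlated: covariance (1 − ρ) divided by variance 2(1 − ρ). This holds for both Hb and QOL, so DE = 1 + (k − 1) × 0.5 × 0.5 for k pairs.

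- k = 2: DE 1.25, type I error 8.0%
- k = 3: DE 1.50, type I error 11.0%

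Simulation with 50 subjects and k = 3 gave about 12%, with an SE ratio of about 1.25.

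**After correction.** With subject-clustered SEs, 150 subjects, m = 4 and no common rise (ρx 0.3 to 0.5, ρe 0.6 to 0.7), simulated type I error was 4.8 to 5.6%, against 10.6 to 17.2% for pooled least squares. In the change fits with 50 subjects, plain clustered SEs still gave about 7%.

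**The case against.** The strongest reply is that pooling is inferred. The SAP is an English translation, the contrast between *each* and *all* is thin evidence, and the output table and figure lists that might settle it are not in the public text. If one regression per visit was intended, no subject counts twice. This stands as a limit on certainty. But the text names no per-visit output for these fits, and two programmers could produce different p-values from it.

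A reader might infer that the p-values are certainly anti-conservative. The documents do not support that. They give no within-subject correlations, and dosing aims at 11.0 to 13.0 g/dL while the Correction cohort enters below 11.0, so a rise in Hb is expected there and can offset the inflation in the Hb-level fits. The offset is limited because 200 of the 300 planned subjects are in the Conversion cohort, where the aim is maintenance. With the 1.5 SD rise confined to the Correction third, or with a 0.5 SD rise in Conversion, simulated type I error was still 13 to 14% at ρx = 0.5.

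A reader might also infer that all subjects enter one fit, or that the SAPs plan to claim that higher Hb improves QOL. Neither is in the text: lines are fitted by arm, and no decision rule uses a slope. The Phase 1 SAP (8.5.4.7) calls secondary and other endpoints exploratory. That explains the lack of multiplicity adjustment, but it does not make a standard error valid.

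**Conclusion.** The point holds on the natural reading of both SAPs. Pooling several visits per subject within an arm, with no subject term, gives standard errors, CIs and p-values that are not valid in either direction and are likely too small. Under the tabulated correlations and no common Hb rise, the 5% test rejects about 8 to 15% of the time in the Phase 1 analysis and 9 to 18% in the final one. The inflation is smaller, or absent, if Hb correlation is weak and Hb rises after baseline. All these sizes rest on assumed correlations. The matter is confined to an exploratory endpoint. The between-group QOL comparison, the primary analysis and the sample size are untouched, so this is a correction worth making rather than a threat to the trial's conclusion.

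**What to change.** State in both SAPs whether visits are pooled.

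- **If pooled:** keep Y = aX + b, and take the slope and intercept standard errors and the p-value from subject-clustered standard errors. Add a small-sample correction for the smaller cohorts. A model with a random subject intercept is an alternative, but it can change what the slope estimates as well as its standard error, so the SAP should say which slope is wanted.
- **Emax fit:** use a bootstrap that resamples subjects for the parameter standard errors and CIs.
- **Change-versus-change fits:** apply the same treatment.
- **If per-visit regressions were intended:** say so and report one slope per visit.

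The cost is a sentence or two in each SAP and a few lines of code. No new data are needed. The p-values will probably be less favourable.

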8.5.4 Statistical analysis issues

8.5.4.1 Adjustment for covariates

In the analysis of efficacy, in order to consider the effect of the measurement value of the first day of the treatment period on the change of each measurement in the group comparison, the analysis using the MMRM should be conducted using the measurement value of the first day of the treatment period as a covariate in the general analysis.

8.5.4.2 Handling of dropout or missing data

Provided in “7. Data handling”.

8.5.4.3 Interim analysis and data monitoring

The statistical analysis plan for the fixed data for the treatment period phase 1 was prepared separately, and the statistical analysis was conducted. In this statistical analysis plan, statistical analysis plan for the final fixed data was prepared.

8.5.4.4 Multicenter trial

For FAS, the following analysis should be conducted for each following endpoint for each facilities. Descriptive statistics of Hb values should be calculated at Week 52 of the treatment period (imputed by the LOCF method) for each treatment group. Descriptive statistics of mean dose of the study drug should be calculated for the Week 48 to Week 52 of the treatment period in the treatment group.

No analysis will be performed for patient cohorts.

8.5.4.5 Subgroup analyses

The following analyses should be conducted for subpopulations based on the stratification factor for each endpoint in the Table below (Table 8.5.4.5.1) in the FAS. Unless otherwise specified, no analysis will be performed for patient cohorts.

(1) Hb value at Week 52 of the treatment period

LSMean, standard error, and 2-sided 95% CI should be calculated for each treatment group using the MMRM (with compound symmetry [CS] for a covariance matrix within subject variance). The point estimate, its standard errors, 2-sided 95% CI, and p-value of the between-group difference (MT-6548 – darbepoetin) of LSMean should be calculated.

(2) 2. Study drug average dosage at Week 48 to Week 52 of the treatment period

Descriptive statistics should be calculated for each treatment group.

(3) With respect to the responder rate at Week 52 of the treatment period (proportion of subjects with increased Hb level by ≥ 1.0 g/dL from the first day of the treatment period), number of responders in subject, the percentage of responders, and 95% of responders in CI (Clopper-Pearson [Exact] method) are provided in by treatment group.

The estimate, its 95% CI (exact method), and p-value (Fisher's exact test) for group difference (MT-6548 – darbepoetin) should be calculated. Only the Correction and Conversion (Hb < 11.0 g/dL) cohorts should be analyzed.

(4) Target Hb achievement rate at Week 52 of the treatment period

The number, proportion, and 95% CI (Clopper-Pearson [Exact] method) for the proportion of subjects with Hb values within the target range (11.0 g/dL to <13.0 g/dL) should be provided for each treatment group. The estimate, its 95% CI (exact method), and p-value (Fisher's exact test) for group difference (MT-6548 – darbepoetin) should be calculated.

Table 8.5.4.5.1 Subgroup analysis of efficacy

Endpoints	Stratification factor	Stratified category
1. Hb values at Week 24 of the treatment period	Sex	Male, Female
2. Study drug average dosage at Week 20 to Week 24 of the treatment period	Age at time of consent (years)	<65, ≥65 <75, ≥75
3. Responder rates at Week 24 of the treatment period	Body weight (kg) on the first day of the treatment period	<60, ≥60
4. Target Hb achievement rate at Week 24 of the treatment period	Body mass index (kg/m ²) on the first day of the treatment period	<25, ≥25

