16.1.9 Documentation on Statistical Methodology

Confidential

operating procedure for randomized key code table preparation and storage. Subjects who are judged eligible to enter the treatment period are assigned to treatment groups in ascending order of the randomization number based on the randomization key code table for each stratification factor, and the treatment groups assigned on the Web registration system are notified. The investigator/coinvestigator should prescribe the study drug of the treatment group notified on the Web registration system. Further details of randomization methods shall be specified in the standard operating procedure for randomization key code table preparation and storage.

Subjects should be randomly assigned in a 1:1 ratio to MT-6548 and darbepoetin groups with the following stratification factors.

- ✓ Correction cohort or Conversion cohort
- ✓ Mean Hb levels during the screening period (mean of the latest two central measurements):
 - Correction cohort: <10.0 g/dL or \geq 10.0 g/dL
 - Conversion cohort: <11.0 g/dL or \geq 11.0 g/dL

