2.5 Rationale for sample size

A total of 300 subjects (150 each for the MT-6548 and darbepoetin groups) should be enrolled in the treatment period. The target sample size for each cohort is shown below.

- ✓ Correction cohort: 100 subjects
- ✓ Conversion cohort: 200 subjects

However, the maximum number of subjects with mean screening period Hb values (mean of 2 most recent central testing facility results) of <11.0 g/dL and ≥ 11.0 g/dL in the screening period in the Conversion cohort should be 120.

[Rationale]

For the primary efficacy endpoint of mean Hb values at treatment period Weeks 20 and 24, the mean Hb value in the darbepoetin group is assumed to be 12.0 g/dL, the difference between the MT-6548 and darbepoetin groups is assumed to be 0 g/dL, and the standard deviation for both is assumed to be 1.78 g/dL. The non-inferiority margin is set at -0.75 g/dL. Calculation of statistical power from these assumptions shows that a sample size of 150 subjects in each group would ensure greater than 95% probability that the mean of mean Hb values in the MT-6548 group and their 95% CI would fall within the target Hb range (≥ 11.0 to < 13.0 g/dL) and non-inferiority could be established.

In addition, the target sample size was set for each of the Correction cohort, Conversion cohort, Conversion (Hb value ≥ 11.0 g/dL) cohort, and Conversion (Hb value < 11.0) cohort so that appropriate evaluation could be made for each cohort.

The assumed standard deviation was set at 1.78 g/dL based on the upper limit of the 80% CI of the standard deviation in the MT-6548 300 mg group at Week 6 in study CI-0021.

3. Endpoints

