8.1 Basic matters

8.1.1 Level of significance and confidence coefficient

When implementing tests, level of significance should be set at 2-sided 5%. CI will be 2-sided with a confidence coefficient of 95%.

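### The efficacy subgroup analyses test treatment inside each of 62 to 66 levels and never test interaction, so heterogeneity goes unassessed and chance p<0.05 levels are very likely

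*SAP*

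**What the plan says.** Final SAP 8.5.4.5 runs its analyses by subpopulation. For Hb at Week 52 it fits an MMRM with compound symmetry and reports "The point estimate, its standard errors, 2-sided 95% CI, and p-value of the between-group difference" of the least squares means. The rate of Hb rises of at least 1.0 g/dL and the rate within target range each get a difference, an exact 95% CI and a Fisher p-value. The responder analysis is limited to the Correction and Conversion (Hb <11.0) cohorts. Mean dose is descriptive only. Phase 1 SAP 8.5.4.6 has the same layout at Week 24.

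Tables 8.5.4.5.1 and 8.5.4.6 list the factors. Four splits apply to the Conversion cohort only: prior ESA type and three prior-dose tertile splits. Two are defined by oral iron or iron-containing binder use at Week 24.

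The general rule is that for tests the "level of significance should be set at 2-sided 5" per cent (Final SAP 8.1.1). The MMRM interactions (Final SAP 8.5.1, Phase 1 SAP 8.5.1) are time by treatment and time by cohort. No treatment-by-subgroup term appears in either SAP or in protocol section 13.3.

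On multiplicity, Phase 1 SAP 8.5.4.7 treats secondary and other endpoints as exploratory and makes no adjustment. Final SAP 8.5.4.6 says only that multiplicity need not be considered. Neither says how subgroup p-values should be read.

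**The concern.** A subgroup analysis asks whether the treatment effect differs between kinds of patient. A p-value inside one level asks whether the difference is zero in that slice, which is another question. One level at p=0.03 beside another at p=0.40 is not evidence that the two effects differ, and two non-significant levels can hide a real difference. Nor does the within-level p-value address the non-inferiority margin.

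The trial is planned on equality of the arms, so scattered p<0.05 levels should be expected from chance. They invite statements that the drug works better or worse in some group, while a true interaction is never assessed.

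The SAPs are also uneven here. Both withhold between-arm tests of Hb by time point in the whole Conversion cohort (Final SAP 8.5.1, Phase 1 SAP 8.5.2). Yet the subgroup tables call for such tests in 13 slices of that cohort (4 prior ESA types plus three sets of tertiles).

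**Working it through.** **Inputs.** SAP 2.5: "A total of 300 subjects (150 each for the MT-6548 and darbepoetin groups) should be enrolled"; "the difference between the MT-6548 and darbepoetin groups is assumed to be 0 g/dL"; "the standard deviation for both is assumed to be 1.78 g/dL"; "The non-inferiority margin is set at -0.75 g/dL". Allocation is 1:1 (SAP 2.3). Two-sided alpha is 0.05 (SAP 8.1.1). No dropout rate or subgroup size is given.

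**The plan's own figure.** SE of the overall difference = 1.78 × √(2/150) = 0.206 g/dL. Power = Φ(0.75/0.206 − 1.96) = 0.954. Simulating the joint condition (non-inferiority, and the MT-6548 95% CI inside 11.0–13.0) also gives 0.954. This agrees with the statement that 150 per arm "would ensure greater than 95% probability".

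**Counting levels.** In table order: 2+2+2+2+2+6+3+3+3+4+3+2+3+3+3+2+2+2+2+4+3+3+3+2 = 66 levels in 24 splits, with age cut twice. Removing the two Week 24 factors leaves 66 − 4 = 62. Reading each of the three complications as yes/no would give 66 + 3 = 69.

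**Chance findings for Hb, true difference 0 in every level.** Expected number = 0.05 × levels. P(at least one), if independent = 1 − 0.95^levels.

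| Levels | Expected | P(at least one), if independent |
|---|---|---|
| 60 (some levels near empty) | 3.0 | 0.954 |
| 62 | 3.1 | 0.958 |
| 66 | 3.3 | 0.966 |
| 69 | 3.45 | 0.971 |

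The same patients recur in every split, so the tests are correlated. A simulation of 4,000 trials (300 patients, SD 1.78, zero difference, pooled t-test in each level) gave a mean of 3.2 levels with p<0.05 and P(at least one) = 0.835 with even subgroup sizes. With skewed sizes it gave 3.1 and 0.842. The sizes are assumed, the factors are taken as independent of each other, and t-tests stand in for the MMRM.

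**All three tested endpoints.** The ceiling is 3 × 62 = 186 p-values and 186 × 0.05 = 9.3 chance findings (198 and 9.9 with all 66 levels). The true number is lower: Fisher's test is conservative, the responder endpoint is confined to two cohorts, and some levels will hold few or no patients. Examples are eGFR ≥60 (entry requires <60 at screening), AST or ALT above 2 times the upper limit (2.5 times or more is excluded at screening), and a prior ESA outside the types listed for entry.

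**With interaction tests instead.** Dropping the two Week 24 factors and making the complications three separate factors gives 24 − 2 + 2 = 24 tests per endpoint, taking the CYP2B6 co-medication as a baseline factor. Expected chance findings for Hb = 24 × 0.05 = 1.2. P(at least one) = 1 − 0.95^24 = 0.71 if independent, and about 0.68 simulated (complications left out).

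For two equal halves, interaction SE = 2 × 1.78 × √(2/150) = 0.411 g/dL. Power for a 0.75 g/dL difference in effect = Φ(0.75/0.411 − 1.96) = 0.45. For 80% power the difference must be (1.96 + 0.84) × 0.411 = 1.15 g/dL.

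**The case against.** The best defence is that none of this is confirmatory. Phase 1 SAP 8.5.4.7 calls secondary and other endpoints exploratory, and the tested subgroup outcomes are of those types. That stands for the Phase 1 SAP and lowers the stakes. It is incomplete, because the waiver there concerns endpoints and time points and does not mention subgroups, the Final SAP does not repeat the label, and a label does not supply the missing test.

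Second, interaction tests have weaknesses of their own: low power, and about 1.2 chance findings over 24 tests. Keeping a 95% CI in each level also leaves about 3 Hb intervals excluding zero by chance. All of this stands. The gain is that the right question gets tested and the table stops flagging levels one by one.

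A reader might infer that chance significant subgroups are certain. They are not: about 84% allowing for overlap, and 95–97% for 60 to 66 levels even under independence. A reader might also take 9 or 10 false positives over three endpoints as the forecast, but that is a ceiling. Nor do the documents support any doubt about the main result, since the primary comparison is made once in the whole FAS.

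**Conclusion.** The point holds as a cheap improvement of low severity. Both SAPs print a between-arm p-value in each of about 62 to 66 levels and specify no test of heterogeneity. For Hb, about 3 chance p<0.05 levels are expected per SAP, and at least one is very likely.

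The expected count rests on extending the plan's zero-difference assumption to every level and to the Week 24 and Week 52 subgroup analyses. The 84% rests also on the assumed subgroup sizes. The power figure rests on the SD of 1.78 g/dL, which the plan took from the upper limit of an 80% CI; a smaller SD would raise power and dropout would lower it. The non-inferiority conclusion is unaffected.

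**What to change.** In Final SAP 8.5.4.5, delete the within-level p-values, keep the per-level estimates with 95% CIs (a forest plot suits), and report one treatment-by-factor interaction p-value per baseline factor. A single model in the whole FAS will not serve for every row, so specify:

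- **Population.** Fit each model where the factor and endpoint are defined: the Conversion cohort for prior ESA type, users of the relevant ESA within it for the dose tertiles, and the Correction and Conversion (Hb <11.0) cohorts for the responder rate.
- **Complications.** Treat hypertension, diabetes and dyslipidemia as three yes/no factors, because one patient can have several.
- **Hb.** Add treatment × factor and treatment × factor × visit, with their lower-order terms, to the MMRM and test the contrast at the target visit. Name that visit: the Final SAP text says Week 52 while its table says Week 24.
- **Binary endpoints.** Replace Fisher's test, which gives no interaction p-value, with a model-based interaction such as logistic regression, exact or Firth where data are sparse.
- **Very sparse levels.** Show them descriptively.
- **Label.** Call the section exploratory. State that intervals and interaction p-values are unadjusted and that a non-significant interaction does not show homogeneity.

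The two Week 24 factors are not baseline factors and fall outside this set.

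The cost is SAP wording and a revised macro, with fewer p-values and no new data. Final SAP 8.5.4.3 says the Phase 1 analysis had already been done, so there the remedy is limited to a note on how its subgroup p-values should be read. The downsides are low interaction power and the 1.2 chance interactions still expected for Hb.
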